 - Percent of patients with blood glucose > 180 mg/dL.
 - Median blood glucose.
 - Percent of time with blood glucose > 180 mg/dL.
2. Rate of recurrent ketogenesis (serum beta-hydroxybutyrate \geq 1.5 mmol/L) within 12 hours (or until time to hospital discharge if less than 12 hours) after discontinuation of IV insulin.
 - Rate of late-recurrent ketogenesis (serum beta-hydroxybutyrate \geq 1.5 mmol/L) 12-18 hours after discontinuation of IV insulin for participants who remain hospitalized for over 24 hours.
3. Frequency of hypoglycemic events while on IV insulin (and within 12 hours after discontinuation of IV insulin) on glucometer or CGM.
 - Glucometer: percent of patients with blood glucose < 70 mg/dL (+/- 2 hours of an "index" hypoglycemic event).
 - CGM: % of time with blood glucose < 70 mg/dL.
4. Rate of blood glucose decrease while on IV insulin on glucometer and CGM within the following time points: 0-2 hours, 2-4 hours, 4-6 hours, >6 hours.
5. Number of participants who needed a decrease in their IV insulin rate (secondary to hypoglycemia).
6. Feasibility of using CGM as a tool for glucose monitoring in DKA.
 - Percent of CGM failures during treatment of DKA.
 - Correlation of CGM to POC glucose monitoring during DKA.

B. Description of Population to be Enrolled:

Eligible patients will be enrolled from Children's Hospital Colorado Emergency Department; a large tertiary care ED and level I trauma center in Aurora, Colorado. These will be patients with either a known diagnosis of T1D presenting in DKA or a new diagnosis of T1D presenting in DKA (see inclusion criteria). Patients will be enrolled either by the PI or a member of the study team (who will be available between the hours of 8:00 am and midnight). Depending on study team member availability, and due to the variability of time of presentation to the ED, patients who present outside of these hours may not be able to be enrolled into the study.

In this study we aim to approach 100 participants, both males and females aged 6-17.99 years, who present in DKA. Assuming 80% of participants approached will be eligible to participate and 60% of eligible subjects will consent to participate, this provides at least 48 subjects, which is needed for 80% power to detect an absolute difference of 40% difference in the rate of rebound hyperglycemia.

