Data from adult studies cannot be directly translated into the care of children in DKA given the increased risk of cerebral edema in children and more concern regarding hypoglycemia (both in the hospital and in an ambulatory setting). Therefore, a study looking at the benefits

and safety of giving glargine early in DKA needs to be completed in children and adolescents. We see a large number of patients across the age range of 6 to 18 years who present in DKA and, therefore, expect to obtain a full age distribution in our study participants. Additionally, it is highly possible that younger children respond to DKA management differently than older children and adolescents, therefore, potential sub-analyses within different age groups may need to be utilized.

Inclusion Criteria:

Children meeting the following criteria will be considered for enrollment:

1. Age 6-17.9 years at time of enrollment.
2. Known history of T1D defined as: ≥ 1 positive autoantibody (IAA, GAD, IA-2, or ZnT8), HbA1c $\geq 6.5\%$, and insulin requirement. Those with a presumed diagnosis of T1D (new onset diagnosis) based on age and presentation will be included in the study and their autoantibody status and HbA1c status will be determined once these results are available. Only those with a diagnosis of T1D (defined above) will be included in the data analysis.
3. Diagnosis of DKA (serum glucose or fingerstick glucose concentration ≥ 200 mg/dL, venous pH ≤ 7.3 and/or serum bicarbonate concentration ≤ 15 mmol/L, and presumed ketonemia or ketonuria). Confirmation of ketonemia or ketonuria will be made once these results are available.

Exclusion Criteria:

The following participants will be excluded from the study:

1. Participants who present in DKA with known conditions that affect neurological function such as: suspected alcohol or drug use, severe head trauma, meningitis, etc., that would compromise routine neurological assessment during DKA treatment.
2. Other known complicating illness or poorly-controlled chronic illness that is known to affect blood glucose levels and/or electrolyte balance such as: chronic renal disease (requiring hemodialysis), chronic liver disease (with evidence of current hepatic dysfunction, coagulopathy, and/or chronic hepatitis), or severe chronic lung disease (requiring the use of oral glucocorticoids).

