In any clinical study unforeseen human factors provide challenges. This current study is based on a previous study in adults (14) with no reported adverse events such as increased hypoglycemia in those given glargine early in DKA management. However, the primary physician or Diabetes Team may decide to change the participant’s DKA management plan and they would, therefore, come off the study protocol. Additionally, the accuracy of a CGM (which samples interstitial fluid) when used in states of dehydration has not been well-studied. However, a number of small studies have shown CGM to be an accurate measure of blood glucose in an ICU setting (21,25). To improve CGM accuracy we will place the CGM only after initial intravascular hydration has been completed and the CGM will be calibrated (if needed) using a POC glucometer at least twice daily. Additionally, we will continue to obtain frequent POC glucometer readings throughout the hospitalization as this will be used to measure our primary outcome.

We have also performed careful power calculations to allow meaningful analyses of our data.

VII. Data Analysis Plan:

Table 1: Power calculations:

| | | | | | |
|---------------------------|-------|-------|-------|-------|-------|
| Significance level | 0.05 | 0.05 | 0.05 | 0.05 | 0.05 |
| Effect size (%) | 20 | 25 | 30 | 40 | 50 |
| Odds Ratio | 2.333 | 2.852 | 3.500 | 5.444 | 9.333 |
| Power (%) | 80 | 80 | 80 | 80 | 80 |
| Total N | 186 | 122 | 84 | 48 | 30 |

Per our power analysis (Table 1), with a total sample size of 48-50 (24-25 per group) we will have 80% power to detect an absolute difference of 40% in rebound hyperglycemia between the two study groups. These power analyses assume that 30% of participants in the early glargine group will experience rebound hyperglycemia. Chi-squared tests will be employed to evaluate whether the difference in rebound hyperglycemia between the two study groups is statistically significant. We will also use logistic regression to adjust for potential confounders (*BMI, sex, age, established T1D versus newly-diagnosed T1D*). Using a blocked and stratified randomization plan we expect to have similar numbers of newly-diagnosed T1D and known T1D patients in each group.

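### The recruitment forecast presents an expected 48 consenting children as a minimum and allows nothing for the plan's own exclusion of unconfirmed type 1 diabetes, so 80% power for the analyzed set is not secured

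*Combined protocol and SAP*

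**What the plan says.** Section IV.B (Description of Population to be Enrolled) starts from a target number of contacts: "In this study we aim to approach 100 participants". It then applies two rates, "Assuming 80% of participants approached will be eligible to participate and 60% of eligible subjects will consent to participate", and concludes that "this provides at least 48 subjects, which is needed for 80% power".

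Inclusion criterion 2 in the same section lets children with presumed new-onset type 1 diabetes (T1D) enter before their autoantibody and HbA1c results are known. It then restricts the analysis: "Only those with a diagnosis of T1D (defined above) will be included in the data analysis". Section IV.C.2.1 places randomization, ideally, during the initial fluid bolus, and plans about 25 children per group.

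Section VII (Data Analysis Plan) states that "with a total sample size of 48-50 (24-25 per group) we will have 80% power" for an absolute difference of 40%, using a chi-squared test. On the event rate it adds: "These power analyses assume that 30% of participants in the early glargine group will experience rebound hyperglycemia".

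Neither the recruitment forecast nor the power section allows for children who are randomized and later left out of the analysis.

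**The concern.** Three things coincide. The forecast is an average but is worded as a minimum. That average equals the required total exactly. And it counts children who consent, whereas the test will be run on children whose T1D is confirmed.

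The 80% eligibility step cannot absorb the later loss, because a child with presumed T1D counts as eligible at entry and is confirmed or not only afterwards. A reader of section IV.B would therefore believe that the analyzed sample will support 80% power for the primary outcome, when the plan has shown this only for an expected enrolled sample with no losses.

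**Working it through.** **Inputs.** From section IV.B: 100 approached, 0.80 eligible, 0.60 consenting. From section VII: significance level 0.05 (taken as two-sided, which reproduces the plan's table), 30% rebound hyperglycemia with early glargine, a 40-point difference and hence 70% in the control group, and a chi-squared test. From section IV.C.2.1: 1:1 allocation. The proportion later excluded, *d*, is **not given** and is an assumption throughout.

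**Step 1: reproduce the plan's total.** With pooled variance under the null and no continuity correction,

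n per arm = [1.960 × √(2 × 0.5 × 0.5) + 0.842 × √(0.3 × 0.7 + 0.7 × 0.3)]² / 0.40² = (1.386 + 0.545)² / 0.16 = 23.31.

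This rounds up to 24 per arm, 48 in total, as stated. The same formula returns the other four totals in the power table (186, 122, 84 and 30). The odds ratio also agrees: (0.7/0.3)/(0.3/0.7) = 5.444.

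**Step 2: the forecast.** 100 × 0.80 × 0.60 = 48.0. If exactly 100 are approached and each independently has a 48% chance of being eligible and consenting, the standard deviation is √(100 × 0.48 × 0.52) = 5.0, the central 95% range is 38 to 58, and P(fewer than 48) = 46%.

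**Step 3: power by number analyzed** (same formula, equal arms).

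| Analyzed | 50 | 48 | 47 | 46 | 45 | 44 |
|---|---|---|---|---|---|---|
| Approximate power | 82.8% | 81.2% | 80.3% | 79.4% | 78.5% | 77.5% |

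Exact power of the uncorrected chi-squared test, by enumerating all outcomes, is 83.6% at 24 per arm, 80.9% at 23 and 77.8% at 22.

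**Step 4: apply an assumed overall exclusion rate to 48 randomized.** Expected number analyzed = 48 × (1 − d).

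| d (assumed) | Analyzed | Approximate power |
|---|---|---|
| 2% | 47.0 | 80.4% |
| 5% | 45.6 | 79.1% |
| 10% | 43.2 | 76.7% |
| 15% | 40.8 | 74.2% |

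Here d is a proportion of **all** randomized children. Confirmation is deferred only for presumed new-onset cases, so d = (new-onset share) × (proportion of those unconfirmed). The documents give neither factor. If half were new-onset (an assumption), 15% overall would mean 30% of new-onset children unconfirmed.

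**Step 5: start from 50 randomized.** Two exclusions (4%) leave 48 and 81.2%. Five (10%) leave 45 and 78.5%.

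**Step 6: number needed to keep 48 analyzed.** Randomize 48/(1 − d), then divide by the plan's 48% yield, rounding up each time.

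| d (assumed) | Randomized | Approached |
|---|---|---|
| 2% | 49 | 103 |
| 5% | 51 | 107 |
| 10% | 54 | 113 |
| 15% | 57 | 119 |

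**The case against.** A reader might infer that the trial will fall short of its stated 80% power. The documents do not support that, for four reasons.

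- **The power statement is conditional and correct.** Section VII says what 48–50 children would give, and that reproduces. No figure is miscalculated.
- **48 is not a cliff edge.** One loss leaves 80.3% by the formula. At 23 per arm the formula gives 79.4% and the exact calculation 80.9%, so the two methods straddle 80%.
- **The exclusion may be small.** Established cases enter on a known history of T1D, and known type 2 diabetes and several glucose-altering drugs are excluded at entry. Only part of the sample is exposed to the later exclusion.
- **There is some slack.** The plan speaks of 48–50 and about 25 per group. Approaching 100 is an aim, not a cap, and section III reports about 150 cases of diabetic ketoacidosis a year at this center. The 46% figure applies only if recruitment stops at exactly 100.

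All of this stands, and it limits the size of the point. It does not remove it. The forecast as written yields 48, not 50; it is called a minimum; and the plan nowhere says that the 48 needed are analyzed children or that recruitment continues until they are reached.

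**Conclusion.** The wording in section IV.B is wrong as it stands. An expected count is presented as a minimum, set equal to the required total, and taken before an exclusion that the plan itself prescribes. The consequence is that 80% power for the analyzed set is **not secured**; it is not shown to be missed.

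The effect is modest. With 48 randomized, approximate power stays at 80% with 2% excluded and falls to 74% with 15% excluded. A shortfall of more than two points below 80% needs about four of 48 (8%) to be excluded. These figures rest on the plan's own 30% and 70% event rates and on exclusion rates assumed here. The 46% chance of fewer than 48 consenting rests only on the plan's rates, independence between children, and exactly 100 approached.

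**What to change.** 1. In section IV.B, describe 48 as the **expected** number consenting from 100 approached.
2. In sections IV.B and VII, say that the 48 needed for 80% power refers to **analyzed children with confirmed T1D**.
3. In section VII, state power over a range of exclusion rates, labelled as assumptions. The step 4 table can serve unless the sponsor has center data on how often presumed T1D is not confirmed.

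Alternatively to item 3, since approaching 100 is an aim, the sponsor may define the recruitment target as 48 analyzed children and let the numbers randomized and approached follow (step 6).

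Items 1 to 3 cost only text, and the stated power becomes slightly less favorable. The alternative costs a few more children: at an assumed 5% to 10% exclusion, 3 to 6 more randomized than 48, and 7 to 13 more approached than 100.

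Keeping every randomized child in the primary analysis would also remove the loss, but it changes the analysis population. That is a separate question and not part of this correction.

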- Upon diagnosis of DKA patients will begin rehydration with standard fluid therapy using an initial IV bolus of 10mL/kg of 0.9% saline.
- Fluid boluses may be repeated at the discretion of the treating physician to restore hemodynamic instability.
- During initial therapy, study personnel will obtain informed consent. .
- Participant Data: basic information such as name, date of birth, race/ethnicity, and diagnosis will be collected.
- Randomization:
 - We will use a blocked, stratified randomization scheme to allocate participants 1:1 to treatment groups. Randomization will be stratified within new onset and existing T1D patients to ensure balance across treatment groups.
 - Ideally, randomization will occur during the initial fluid bolus, however, if this is not possible then the patient will be treated with the standard DKA protocol for this study site until consent is completed, but not beyond the time frame outlined in the exclusion criteria.
 - Participants will be randomized into one of two groups:
 - 1. Early glargine, study group (N ~ 25):**
 - a. Administer glargine SQ x 1 when pH \geq 7.10.
 - b. Primary investigator and/or on-call co-investigator to determine glargine dose:
 - i. New onset T1D: 0.3 units/kg
 - ii. Established T1D: use home total daily dose (TDD) of long-acting insulin (or TDD of basal if on an insulin pump), converted to glargine equivalents.
 - 2. Standard-of-care, control group (N ~ 25):**
 - a. Administer glargine SQ x 1 at time of correction of acidosis (venous pH \geq 7.3 and serum bicarbonate \geq 18 or BHB \leq 1) and discontinuation of IV insulin.
 - b. Primary investigator and/or on-call co-investigator to determine glargine dose as described above.
- After initial fluid bolus(es), standard insulin therapy begins with a continuous infusion of IV regular insulin at a rate of 0.1 units/kg/hr.
- Ongoing rehydration is established using IV fluids with $\frac{3}{4}$ normal saline at a standard rate of 1.5 x maintenance unless this is determined to be harmful by the primary attending physician.
- Potassium replacement is provided using IV fluids containing potassium acetate and potassium phosphate.
- When serum glucose concentration declines below 250 mg/dL, dextrose (5-12.5%) is added to the IV fluids to maintain serum glucose between 100 mg/dL and 200 mg/dL.

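### Age sub-analyses within age groups, if read as separate tests, would not show whether the effect of early glargine differs by age; one exploratory treatment-by-age interaction would address that question directly

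*Combined protocol and SAP*

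**What the plan says.** Section IV.B (Description of Population to be Enrolled) argues that "it is highly possible that younger children respond to DKA management differently than older children and adolescents" and concludes that "potential sub-analyses within different age groups may need to be utilized". It gives no number of age groups, cut-points, test, rule of interpretation or exploratory label.

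Section VII (Data Analysis Plan) compares rebound hyperglycemia between the two arms with a chi-squared test and then states: "We will also use logistic regression to adjust for potential confounders". Age is one of the four covariates listed there, with BMI, sex and established versus new T1D. No treatment-by-age term appears. Under Randomization in C.2.1, allocation is stratified by new-onset versus existing T1D, not by age. Age differences are not part of any hypothesis, aim or listed outcome.

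**The concern.** Whether younger children respond differently to early glargine is a question about a difference between effects. A test within each age group asks something else: whether there is evidence of an effect in that group alone. With about a dozen children per arm in a group, each test has roughly even odds of reaching significance at the planned effect. One significant and one non-significant group is then an ordinary result even when the effect is identical. Putting age in the regression as a covariate does not help, because that assumes a common treatment effect across ages.

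At stake is a mistaken statement that early glargine works at some ages and not at others. Section III says that no exclusively pediatric data exist on these outcomes, so such a statement could carry weight. Because the groups are not fixed, the cut-points could also be chosen after the data are seen.

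**Working it through.** **Inputs from the documents.** Section VII: level 0.05; 30% rebound hyperglycemia with early glargine ("These power analyses assume that 30% of participants in the early glargine group will experience rebound hyperglycemia"); a 40-point difference, hence 70% in controls; total N 48-50. C.2.1: 1:1 allocation. Section III: adult-study rates of 33.3% v 93.5%.

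**Assumptions.** Two equal age groups with 12 children per arm in each (24/2), because the plan names no groups. Tests are two-sided.

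**Step 1. Reproduce the plan's N.** With pooled variance and no continuity correction,

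n per arm = [1.96 × √(2 × 0.5 × 0.5) + 0.8416 × √(0.3 × 0.7 + 0.7 × 0.3)]² / 0.40² = (1.386 + 0.545)² / 0.16 = 23.3, rounded up to 24, or 48 in total.

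This matches Section VII. The other columns of its power table (186, 122, 84, 30) reproduce in the same way. A one-sided test would give 38, so the plan's calculation is two-sided.

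**Step 2. Same effect in both age groups.** Let P be the power within one group, by exact binomial enumeration. The chance that exactly one of two groups is significant is 2P(1 − P), which cannot exceed 50% when the groups have equal power.

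| Common effect | P, chi-squared | Exactly one | P, Fisher | Exactly one |
|---|---|---|---|---|
| 30% v 50% | 0.190 | 31% | 0.094 | 17% |
| 30% v 60% | 0.357 | 46% | 0.211 | 33% |
| 30% v 70% (plan) | 0.565 | 49% | 0.389 | 48% |
| 30% v 80% | 0.768 | 36% | 0.610 | 48% |
| 33.3% v 93.5% (adult study) | 0.933 | 13% | 0.849 | 26% |

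At the plan's rates with chi-squared: 2 × 0.565 × 0.435 = 0.492. Both groups are significant in 0.319 of trials and neither in 0.189.

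Unequal splits at the plan's rates (10/14, 8/16 and 6/18 per arm) give 51-60% with chi-squared and 45-59% with Fisher. Three groups of 8 per arm give mixed results in 74% (chi-squared) or 56% (Fisher).

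**Step 3. No effect at any age.** The chance of at least one falsely significant group is 1 − (1 − s)², where s is the exact size of the test at 12 per arm.

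- Chi-squared, event rate 30% or 70%: s = 0.049, giving 9.6%. At 50%: s = 0.064, giving 12.4%.
- Fisher, event rate 30% or 70%: 3.4%. At 50%: 4.5%.

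**Step 4. The interaction test instead.** With 30% v 70% at every age and age uniform on 6-18, a treatment-by-continuous-age term in a logistic model was falsely significant in 4.2% (Wald) to 6.5% (likelihood ratio) of 8,000 simulated trials.

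**Step 5. Its power.** For two equal age groups on the risk-difference scale, with event rates of 30% or 70% in every cell,

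SE of the difference between the two effects = √[2 × (0.21 + 0.21)/12] = √0.07 = 0.265.

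Power for a 40-point difference in effect = Φ(0.40/0.265 − 1.96) = Φ(−0.45), about 33%. A power of 80% needs (1.96 + 0.8416) × 0.265, about 74 points. This is a two-group guide; the power of the continuous-age logistic term was not computed.

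**The case against.** The sentence in IV.B is tentative and sits in the reasoning for enrolling a wide age range. A reader might infer that the trial has committed to a significance test in each age group and will read a split result as a difference. The documents do not say so. The sub-analyses could be descriptive rates or estimates with intervals, and Section VII assigns the chi-squared test to the two arms, not to age bands. This objection stands, and it is why the point is conditional.

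A reader might also take one half as a general rate of split results. It is not: the figure belongs to the planned 40-point effect with two groups, and it is close to the 50% ceiling. Nor do the calculations support a general claim that testing two groups raises the false-positive rate above 5%. That happens with the uncorrected chi-squared test but not with Fisher, a natural choice in groups this small.

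Finally, the interaction has little power in 48 children, so it will seldom settle the question either. That also stands. It does at least test the right quantity, and it gives a false age signal in about 4-7% of trials where separate tests give a split result in about half. Low power is a reason to report an estimate with its interval, not to fall back on subgroup p-values.

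**Conclusion.** The point holds in conditional form. Within-group sub-analyses are the only approach the plan offers for a difference that it regards as quite possible, and no planned analysis compares the effect across ages. If they are carried out as separate tests, a split result is expected in about 48-49% of trials at the plan's own effect with two equal groups. The two-group range is 13% to 49% with chi-squared and 17% to 48% with Fisher over the effects tabulated above.

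The conclusion rests on an assumed number of groups, equal group sizes and a common effect at all ages. It does not extend to the primary comparison, the sample size or any listed outcome. It is a worthwhile, inexpensive improvement to a tentative secondary analysis.

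**What to change.** Replace the sentence in IV.B, and add the same text to Section VII, along these lines:

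> Any difference in effect by age will be examined by one treatment-by-age interaction, with age continuous, in a logistic model for the primary outcome. This analysis is exploratory and will be reported with its 95% confidence interval. Results by age band, if shown, will be estimates with confidence intervals, without separate significance tests. Power for this interaction is low at the planned sample size, so a non-significant result will not be taken to show that the effect is the same at every age.

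The cost is a few sentences in two places. Age is already available from the date of birth, and the sample size, primary test and treatment are unchanged. There are two downsides to accept: the low power shown above, and the assumption that the log odds ratio changes linearly with age.
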